3.3 Study Duration and Dates

Actual overall study duration or participant recruitment period may vary. The proposed study start is Q4 2021. A participant's time on the study is expected to last 5 weeks from enrollment. Subject participation will consist of 5 days of Screening/Baseline, and 28 days study treatment, followed by 7 days of Follow-Up for safety assessments. Participants should complete the study on Day 35.

For participants that test positive for COVID-19, Health Canada (HC)/FDA, or other applicable relevant local/national regulatory health authorities should be notified as applicable to the regional area. Participants that test positive for COVID-19 will be encouraged to complete early termination assessments and record their symptoms using the COVID-19 symptom list.

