9.5 Analysis of Efficacy

9.5.1 Primary Efficacy Analysis

The primary efficacy objective is to demonstrate that NONS product reduces the risk of COVID-19 infection. The associated null hypothesis is that the hazard ratio (HR) of NONS relative to placebo is greater than 1, or H_0 : $HR \ge 1$, or equivalently in terms of a vaccine efficacy, H_0 : $VE \ge 0$ where vaccine efficacy is calculated as VE = 100% x (1-HR). The HR will be estimated using a Cox proportional hazard regression model with a fixed effect only for treatment arm. Due to the small, expected event rate (see the Section 9.2), incorporation of additional fixed effects may not be possible. However, as a sensitivity analysis, a stratified Cox model using randomization strata (≥ 65 , <65 at increased risk, < not at increased risk) will also be fit. Similarly, age-group (\ge /<65) and region-specific models will be fit, aggregating adjacent provinces, states, or larger geographies to enable model convergence and evaluate, to the extent possible, whether differences exist.

The primary analysis will be executed in the mITT data set and count all cases occurring starting from the day after participants begin administering study treatment.

For all models, a 2-sided score-based 95% confidence interval (CI) and 2-sided p-value for the effect of NONS will be calculated.

The estimand of the primary analysis is a treatment policy strategy and will consider intercurrent events as censored. Specifically, participants who stop administering NONS for any reason, stop submitting data to the electronic patient-reported outcomes (ePRO) system, do not submit paper diaries, or are unreachable by telephone contact, will be censored on the day of their last ePRO clinical status submission or last available documented day on paper diary (ie, the last day confirming no positive COVID-19 test). Participants who submit COVID-19 test results following Day 28, will be censored at Day 28. Participants submitting a COVID-19 test result on or prior to Day 28 will be considered to have reached the primary endpoint on the day that the specimen (ie, nasal swab) is collected, not the date of the test. Positive test results obtained within 48 hours of randomization will be considered infected at randomization and not counted as events.

The Cox model will be fit to the following sets (if different) as sensitivity analyses:

- mITT set counting all cases after randomization,
- PP set counting cases after first administration,

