- PP set counting all cases after randomization, and
- Randomized set counting all cases after randomization

The primary analysis will be repeated in the following subgroups:

- Subjects unvaccinated against SARS-CoV-2 prior to randomization
- Subjects partially vaccinated against SARS-CoV-2 prior to randomization
- Subjects fully vaccinated against SARS-CoV-2 prior to randomization
- Subjects who are fully vaccinated and have received a booster shot against SARS-CoV-2 prior to randomization
- Subjects who become partially vaccinated against SARS-CoV-2 during the course of the study
- Subjects who become fully vaccinated against SARS-CoV-2 during the course of the study
- Subjects who receive a booster vaccine against SARS-CoV-2 during the course of the study

Specific procedures to account for missing data, unused or spurious data and criteria for termination will be delineated in the SAP. Procedures for reporting any deviation(s) from the original statistical plan will be described in the SAP and justified (if needed) in the final clinical study report.

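### Three of the seven vaccination subgroups are defined by vaccination after randomisation, while case counting starts the day after first dose

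*Combined protocol and SAP*

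**What the plan says.** Section 9.5.1 states "The primary analysis will be repeated in the following subgroups" and lists seven groups. Four are fixed by vaccination status before randomisation. Of the other three, one is "Subjects who become partially vaccinated against SARS-CoV-2 during the course of the study". Another is defined as "Subjects who become fully vaccinated against SARS-CoV-2 during the course of the study", and the last as "Subjects who receive a booster vaccine against SARS-CoV-2 during the course of the study".

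The analysis to be repeated is described in the same section: "The HR will be estimated using a Cox proportional hazard regression model with a fixed effect only for treatment arm". It is to "count all cases occurring starting from the day after participants begin administering study treatment", and the efficacy window closes at Day 28: "Participants who submit COVID-19 test results following Day 28, will be censored at Day 28". A 95% confidence interval and p-value are promised for every model. No landmark, delayed entry, time-varying vaccination status or cautionary note is given for the three on-study groups.

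The study itself runs longer than the efficacy window. Section 3.3 says "Participants should complete the study on Day 35".

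**The concern.** Membership of the three groups becomes known only during follow-up, but each member's case counting begins at the start of treatment. To be recorded as vaccinated on, say, Day 20, a participant must usually still be in the study on Day 20. Section 3.3 encourages those who test positive to do the early termination assessment, section 3.3.1 treats that assessment as completing the study, and section 6.6.5 expects some participants to leave because of infection. Section 9.2 also assumes 25% censoring over 28 days. People infected or lost early will therefore seldom appear in these groups, and the time their fellow members spent before vaccination is largely event-free because of how the group was formed.

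Three things follow. Infection rates in these groups will look too low. They cannot be read beside those of the four groups fixed before randomisation. Membership is also an outcome observed after randomisation, so balance between arms is no longer guaranteed. Finally, someone vaccinated on Days 29-35 joins a group after the whole efficacy window has closed, and so contributes only pre-vaccination time.

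**Working it through.** **Inputs from section 9.2:** HR 0.15; two-sided 0.05; 90% power; placebo daily incidence 0.000075; 11,480 participants randomised 1:1 (5,740 per arm); 1.05% loss per day. **Assumed, because the documents are silent:** on-study uptake of 5%, 10% or 30% per subgroup; vaccination days uniform over Days 0-28 or 0-35; no effect of the vaccine on infection risk.

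**1. The plan's own figures.** Schoenfeld events = 4(1.960 + 1.282)² / (ln 0.15)² = 11.68, rounded up to 12. Let λ = 0.000075 for placebo and 0.15 × 0.000075 = 0.00001125 for NONS, and let the loss hazard be c = −ln(1 − 0.0105) = 0.010556. Retention at Day 28 is exp(−28c) = 74.4%, in line with 25% censoring. Events per arm = 5,740 × λ/(λ+c) × [1 − exp(−28(λ+c))] = 10.43 placebo and 1.57 NONS, total 11.99. The stated 10 and 2 are reproduced.

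**2. Event-free share of person-time, if infected participants are never recorded as vaccinated.**

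- Uniform over Days 0-28: mean vaccination day 14, so 14/28 = 50%.
- Uniform over Days 0-35: 28/35 of members have a mean of 14 event-free days and 7/35 have all 28, so (0.8 × 14 + 0.2 × 28)/28 = 16.8/28 = 60%.
- With the plan's dropout included, the shares are 49.9% and 58.9%. The apparent placebo rate is 0.50 or 0.41 of the true rate.
- If infected participants stay and are vaccinated on the same schedule as others, the share falls towards zero.

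**3. Effect on the HR between arms.** This is the large-sample solution of the Cox score equation in the subgroup, under the same total exclusion and with vaccination over Days 0-28.

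- Same timing in both arms: a true HR of 1.00 stays at 1.00, and 0.15 becomes 0.14998.
- Different uptake only (5% against 15%): a true HR of 1.00 stays at 1.00.
- Timing differs by arm (one arm's density falling linearly over Days 0-28, the other's rising): a true HR of 1.00 becomes 0.50 if placebo participants are vaccinated earlier, and 2.01 if NONS participants are.
- Counting person-time only from vaccination returns the true HR in every case.

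Selection on staying uninfected is itself small at the planned rate: 1 − exp(−14 × 0.000075) = 0.10% of placebo participants by Day 14, and 0.21% by Day 28.

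**4. Information in each subgroup.** With a = λ + c, uptake u and vaccination uniform over Days 0-28, expected events per arm under total exclusion = 5,740 × u × (λ/a) × [(1 − e^(−28a))/(28a) − e^(−28a)]. For placebo at u = 10%: 574 × 0.007055 × (0.8649 − 0.7426) = 0.50.

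| Uptake | Placebo | NONS | Total | Chance of no event |
|---|---|---|---|---|
| 5% | 0.25 | 0.04 | 0.29 | 75% |
| 10% | 0.50 | 0.07 | 0.57 | 57% |
| 30% | 1.49 | 0.22 | 1.71 | 18% |

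At 8.23% a year, the highest annualised rate quoted in section 9.2, and 10% uptake, 1.49 + 0.22 events are expected. With no exclusion of infected participants, and uptake unrelated to infection risk, the planned-rate totals cannot exceed u × 11.99: 0.6, 1.2 and 3.6 events.

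**The case against.** The strongest reply is that nothing bars vaccination after a positive test. Early termination is only encouraged, and Table 4 collects concomitant medications daily through Day 35. Someone infected on Day 5 and vaccinated on Day 30 would qualify as the text stands. This is right. A reader might infer that all pre-vaccination time is event-free by construction, and the documents do not support that: the exclusion is practical and partial. The 50% and 59% are therefore the total-exclusion cases under assumed timing.

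Second, the planned output is an HR between arms within each subgroup. No comparison of rates across subgroups is specified, and the HR hardly moves when both arms share the same vaccination timing. This also stands. A reader might infer that these subgroup HRs are seriously biased. That would need timing to differ by arm, and nothing in this double-blind design shows that it would.

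Third, a participant can fall into more than one of the seven groups. That is not an error, since section 9.5.1 does not present them as a partition.

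Fourth, section 9.1 promises a separate detailed SAP that might handle this, and its text is not available here. But section 9.5.1 leaves to it missing, unused or spurious data, termination criteria and the reporting of deviations. It does not expressly leave it the handling of these subgroups, so the protocol as written prescribes the analysis.

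**Conclusion.** The concern holds in a limited form. Three supportive subgroup analyses condition on an event after randomisation and start counting before that event, with no method to deal with it. The consequence is mainly misleading subgroup event rates: as low as 0.50 of the true rate (vaccination over Days 0-28) or 0.41 (Days 0-35) if infected participants are never recorded as vaccinated, and closer to the truth the more of them are. The arm HR is at risk only under differential timing. The primary mITT conclusion is not affected.

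The groups would also tell the reader little. At planned rates and up to 30% uptake, fewer than 2 events are expected per group under total exclusion, and at most 3.6 without it. With no events there is no HR to estimate; with events in one arm only, the estimate sits at its boundary. The promised intervals and p-values will often be unobtainable or uninformative. All these sizes rest on assumed uptake and timing.

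**What to change.** In protocol section 9.5.1, and in the SAP to match:

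- Delete the three subgroups defined by on-study vaccination and keep the four defined before randomisation.
- Add one sensitivity analysis of the primary Cox model that censors each participant at the first SARS-CoV-2 vaccine dose received on study. It adds no model parameter. State that it assumes vaccination is unrelated to later infection risk within arm.
- If on-study vaccinees are of interest, list their events descriptively by arm, with person-time counted from the vaccination date.

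A time-dependent vaccination covariate would remove the event-free time in principle, but it suits about 12 events poorly. Section 9.5.1 itself doubts that further fixed effects can be fitted, and a main effect for vaccination would not estimate the NONS effect among those vaccinated on study.

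No new data are needed: sections 5.6 and 7.11 already have vaccinations recorded. The cost is a small wording amendment, which needs IRB/IEC approval under section 10.1, and the loss of three near-empty subgroup outputs. It should be made before unblinding.

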9.5.2 Secondary Efficacy Analysis

For the secondary objective of prevention of medical intervention for COVID-19, the secondary endpoint will be executed similarly to the primary efficacy analysis above.

Participants who are hospitalized for COVID-19-related symptoms, but who test negative for COVID-19 will not be considered to have met the endpoint. The time of the endpoint will be considered the study day at which the participant was hospitalized or the day at which the ER/ED visit occurred even if a COVID-19 positive result was obtained before or after the day of the event.

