- 8. Participants who have any other condition that, in the opinion of the Investigator, would interfere with a participant's ability to adhere to the protocol (eg, participants whom are mentally or neurologically disabled and whom are considered not fit to their participation in the study), interfere with assessment of the investigational product, or compromise the safety of the participant or the quality of the data.

Planned Number of Participants: 13,000 to be randomized with a maximum of 11,480 participants initiating study treatment.

Test Product, Dose, and Mode of Administration: The test product is nitric oxide (NO) releasing solution delivered in the form of a nasal spray which will be self-administered three (3) times per day, morning, noon, and night for 28 days.

The comparator is a placebo of saline solution to be self-administered as the test product.

Duration of Treatment: Participants will be on study for 5 weeks (to include 1 week of screening/baseline, 4 weeks of treatment, 1 week of Follow-Up).

Efficacy Assessments: Participants will self-assess COVID-19-related symptoms, report if they have tested positive for COVID-19, and report if they need hospitalization or an ER visit. A positive COVID-19 test can be either by antigen or SARS-CoV-2 RT-PCR.

Safety Assessments: Adverse events (AEs) and discontinuations of treatment will be collected, and the number of participants that are hospitalized or visit the ED or ER for COVID-19/flu-like symptoms.

Study Endpoints: Primary Endpoint: Confirmed positive COVID-19 test (Both antigen and SARS-CoV-2 RT-PCR are acceptable) by Day 28.

Secondary Endpoint: Hospitalization or ER/ED visits for COVID-19/flu-like symptoms by Day 28.

Safety Endpoint: AEs and discontinuation of treatment.

Statistical Methods:

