2.2 Secondary Objectives and Endpoints

Objective	Endpoint	
To assess the efficacy of NONS in prevention of severe COVID-19	Hospitalization or ER/ED visits for COVID-19/flu-like symptoms by Day 28	
Assess tolerability of NONS in participants with all participants including those with COVID-19	AEs and discontinuation of treatment	

Abbreviations: AE=adverse events; ER/ED=emergency room, emergency department NONS=nitric oxide nasal spray.

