3 INVESTIGATIONAL PLAN

3.1 Overall Study Design and Plan

This is a multicenter, randomized, double-blinded, placebo controlled, Phase 3 clinical efficacy study evaluating NONS in healthy adult volunteers as a prevention treatment for individuals at risk from COVID-19 infection.

Up to 13,000 adult participants aged 18 or over with no known history of SARS-CoV-2 infection will be randomized into one of two cohorts of this study in a ratio of 1:1 (Treatment: Placebo Control). Participants with or without underlying medical conditions will be eligible to enroll. The NONS formulation proposed for use in this COVID-19 clinical study will be self-administered at a maximum of 3 times per day, morning, noon, and night for 28 days. Participants will be on study for 4 weeks of treatment (to include 5 days of Screening, 1 week of Follow-Up, participants will be followed for a total of approximately 5 weeks) as a viricidal Investigational Medical Product.

Participants will self-administer a nasal spray containing either blinded study treatment or placebo (herein called study treatment). Nitric oxide nasal spray (NONS) will be delivered from manual pump nasal spray container with 25 mL of solution with each nasal spray dispensing approximately 130-150 μ L of solution. After the subject blows their nose, each treatment will require two sprays per nostril, or about 0.5 mL per treatment.

The primary endpoint is to assess the efficacy of NONS in the prevention of COVID-19 infection as determined by a positive COVID-19 test (antigen or reverse-transcriptase polymerase chain reaction [RT-PCR]),

The secondary endpoints are to determine the proportion for participants requiring hospitalization or emergency room (ER/emergency department [ED]) visits for COVID-19 or flu-like symptoms by Day 28 and assess the safety and tolerability of use of NONS in participants with COVID-19.

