13 APPENDICES

Appendix 1 Schedule of Events

Table 4 Schedule of Events

	Screening a Baseline	Daily on TX	Early TX Day	Last Tx Day	Post-Tx Follow-up		
Assessments			Phone Assessment 1	Phone Assessment 2	Phone Assessment 3	ET	
Visit Type (per specific country regulatory legislation)	Remotely or On-Site	Remotely	Remotely	Remotely	Remotely or On-Site	Remotely or On-Site	
Study Day	-7 to 1	1-35 ^d	7+3	28 +2	End of Study 35±3		
Participant Informed Consent (Virtual, if applicable/respective country) b	X						
Demographics (Virtual, if applicable/respective country)	X						
Medical History (Virtual, if applicable/respective country)	X						
Clinical Exam including Vitals (Virtual, if applicable/respective country)	X				X	X	
Pregnancy Test (Urine) ^c	X				X	X	
Concomitant Medications ^d	X	X	X	X	X	X	
Randomization	X						
Study treatment instructions ^e	X		X				
COVID related symptom assessment ^f			X	X	X	X	
NONS Self Administration ^g		X	X	X			
Questionnaire (online/paper) h		Xi	X	X	X	X	
Adverse Events		X	X	X	X	X	
Study Drug Accountability/Compliance		X	X	X		X	
Report if tested positive for COVID-19 infection		X	X	X	X	X	
Report need for Hospitalization/ER Visit for COVID-19 related sequelae		X	X	X	X	X	

Abbreviations: ER=emergency room; ET= early termination; NONS= nitric oxide nasal spray; Tx=treatment.

NONS (nitric oxide nasal spray)
Clinical Trial Protocol: COVID-NONS-04

- ^a Screening and baseline are to be taken within 7 days but may be taken at the same assessment. Post-Treatment Follow-up visits (end of study and ET) may be performed remotely. For countries requiring an in-person visit, these will be performed on-site, unless the participant is hospitalized, in quarantine or unable to visit the site for any reasonable cause as per the investigators' judgement; these visits may then be performed remotely and will not be considered a protocol deviation. Follow-up of all adverse events must be completed as described in the protocol Section 7.
- Participants will be asked to designate an emergency contact who will also sign informed consent. In the event the participant is hospitalized and cannot complete their treatment diary or questionnaire emergency contacts will be encouraged to provide symptoms on behalf of a participant in a COVID-19 symptoms list Diary (Appendix 2).

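### The only secondary efficacy endpoint is defined inconsistently: Section 2.2 sets no test condition, while Section 9.5.2 excludes test-negative admissions, does not name ER/ED visits in that exclusion, and gives no rule for untested participants

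*Combined protocol and SAP*

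**What the plan says.** Section 2.2 pairs the objective "To assess the efficacy of NONS in prevention of severe COVID-19" with the endpoint "Hospitalization or ER/ED visits for COVID-19/flu-like symptoms by Day 28". The synopsis, under study endpoints, uses the same wording. Section 3.1 writes the slash out as a plain alternative: "visits for COVID-19 or flu-like symptoms by Day 28". None of these places mentions a test result. The other item in Section 2.2, "AEs and discontinuation of treatment", concerns tolerability, so this is the only secondary efficacy endpoint.

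Section 9.5.2 adds a test condition: "Participants who are hospitalized for COVID-19-related symptoms, but who test negative for COVID-19 will not be considered to have met the endpoint". The sentence names hospitalised participants only. The next sentence sets the event date as the day of admission or "the day at which the ER/ED visit occurred even if a COVID-19 positive result was obtained before or after the day of the event".

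Data collection is worded more narrowly. The relevant row of Table 4 is "Report need for Hospitalization/ER Visit for COVID-19 related sequelae", and Section 6.6.2 has staff ask about visits that resulted from COVID-19. Section 6.6 is unqualified but refers to Table 4 for the detail. The synopsis paragraph on safety assessments does include flu-like visits.

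**The concern.** The endpoint definition and the analysis rule select different events. Read literally, Section 9.5.2 also applies the stricter rule to admissions and the looser one to ER/ED visits, although Section 2.2 states the aim as preventing severe disease.

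Every version of the objective is specific to COVID-19: medical intervention resulting from COVID-19 (synopsis), severe COVID-19 (Section 2.2) and medical intervention for COVID-19 (Section 9.5.2). Flu-like visits with another cause do not bear on it. If NONS does not affect them, they pull the HR toward 1. If it did prevent other respiratory infections, which the broad-spectrum rationale in Section 3.2.2 leaves open, those prevented visits would be credited as prevention of severe COVID-19. With so few infections expected, a handful of such visits could decide the estimate. Leaving the rule open also leaves the event set to be chosen later.

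**Working it through.** **Step 1. The rules side by side.**

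| Visit for COVID-19 or flu-like symptoms | Synopsis, 2.2, 3.1 | 9.5.2 as worded |
|---|---|---|
| Admission, test positive | event | event |
| Admission, test negative | event | not an event |
| ER/ED visit, test positive | event | event |
| ER/ED visit, test negative | event | not named in the exclusion; timing sentence presupposes a positive result |
| Either, never tested | event | no rule |

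The second row is a direct contradiction. The last two are gaps. The untested row is a realistic case: Table 4 schedules no SARS-CoV-2 test and lists only the reporting of positive results.

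**Step 2. The plan's own event count (primary endpoint, Section 9.2).** Inputs: 5,740 per arm, placebo hazard h = 0.000075 per day, HR 0.15, loss g = 0.0105 per day, 28 days.

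- Expected events per arm = n × h/(h+g) × (1 − exp(−28(h+g))).
- Placebo: 5,740 × 0.000075/0.010575 × (1 − exp(−0.2961)) = 10.43.
- NONS, with h × 0.15 = 0.00001125: 1.57.
- Total 12.0, against the stated 10 and 2. Schoenfeld's formula requires (1.960 + 1.282)² / (0.25 × (ln 0.15)²) = 11.68, rounded up to 12; power at 12 events is 0.908. The stated figures reproduce.

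The documents give no figure for the secondary endpoint.

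**Step 3. Illustration of dilution.** None of the following assumptions comes from the documents:

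- 5% to 20% of the 12 infections lead to a visit, so T = 0.6 to 2.4 true events.
- True events follow HR 0.15: placebo T/1.15, NONS 0.15T/1.15. That gives 0.52 and 0.08 at T = 0.6, and 2.09 and 0.31 at T = 2.4.
- Off-target visits are observed in 0.01% to 0.1% of 11,480, so B = 1.15 to 11.48, split equally between the arms (no NONS effect).
- The ratio of arm counts stands in for the HR: (B/2 + NONS)/(B/2 + placebo).

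| | T = 0.6 | T = 2.4 |
|---|---|---|
| B = 1.15 | (0.574+0.078)/(0.574+0.522) = 0.60 | (0.574+0.313)/(0.574+2.087) = 0.33 |
| B = 11.48 | (5.74+0.078)/(5.74+0.522) = 0.93 | (5.74+0.313)/(5.74+2.087) = 0.77 |

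The off-target share B/(B+T) runs from 32% (B = 1.15, T = 2.4) to 95% (B = 11.48, T = 0.6).

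**The case against.** The sponsor can say that Section 9.5.2 simply refines Section 2.2. It opens by limiting the aim to COVID-19, and its timing sentence makes sense only if a positive result is expected for ER/ED visits as well as admissions. This has force. A reader might infer that the plan definitely counts test-negative ER/ED visits, or untested participants, in the analysis. The documents do not support that: the timing sentence points the other way, and for untested participants Section 9.5.2 gives no rule. But the timing sentence dates an event and does not make a positive result a condition. Even if it did, Section 9.5.2 would still contradict the synopsis and Sections 2.2 and 3.1.

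A reader might also infer that non-COVID flu-like visits will supply most of the events. That is not shown. Table 4 and Section 6.6.2 prompt only for visits due to COVID-19, which should limit how many others are recorded, and the off-target rate is assumed. The assumption of no NONS effect on other flu-like illness is also ours; Section 3.2.2 says the dose rests partly on in-vitro work with influenza viruses.

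The consequence is limited too. With 0.6 to 2.4 expected true events the endpoint carries little inference under any definition: three events, all on placebo, give an exact binomial two-sided p of 2 × 0.5³ = 0.25. This is why the point should not be given more weight than a secondary endpoint warrants. It does not remove the contradiction.

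Section 9.1 defers detail to a separate statistical analysis plan. The document available contains no text from such a plan that settles this.

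**Conclusion.** The inconsistency is real and does not depend on any rate. The endpoint sections and Section 9.5.2 treat test-negative admissions differently, the exclusion sentence does not name ER/ED visits, untested participants have no rule, and the collection prompts are narrower than the endpoint they serve.

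The numerical effect cannot be fixed from the documents. Under the assumptions in the working, a true HR of 0.15 would be observed as about 0.33 to 0.93. That range shows sensitivity to a few off-target visits and is not a forecast. The point should be corrected, but it concerns one secondary endpoint with very few expected events. Nothing here touches the primary endpoint, the 11,480 sample size or the 90% power.

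**What to change.** Put one definition in the synopsis and Sections 2.2, 3.1 and 9.5.2: an admission or ER/ED visit for COVID-19 symptoms by Day 28 with a positive SARS-CoV-2 test, antigen or RT-PCR, obtained before or after the visit. Apply the same test rule to admissions and ER/ED visits.

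State that untested visits are not events in the main analysis, and count them as events in a sensitivity analysis. Report other flu-like visits descriptively. Align the Table 4 wording, and the matching question in Section 6.6.2, so that these visits are asked about and so that a negative result can be told apart from no test. Settle the definition before unblinding.

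The cost is mainly wording, plus a change to the collection items if the Manual of Procedures does not already cover them. There are two downsides: fewer secondary events, and true COVID-19 visits that were never tested are missed in the main analysis. The sensitivity analysis shows how much the second one matters.
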